Although the efficacy of FMT appears convincing, there is a paucity of robust safety data for FMT. The current safety profile has been collected predominantly from retrospective reviews or systematic reviews of case series data, approaches that have methodological limitations in assessing the safety of FMT.^{21 24 25} Broadly, the literature contains inconsistent long-term follow-up of adverse events, which have been spontaneously reported rather than actively sought, in turn increasing the risk of underreporting. ²¹ Randomized controlled trials have also had brief follow-up and one trial was stopped early for benefit at interim analysis, limiting the ability to meaningfully assess the long-term safety profile of FMT.^{22 23} Although the current body of literature does not signal any significant safety risk for FMT, a high-quality prospective longitudinal study is needed to confirm the safety profile of FMT among recurrent CDI patients.

OpenBiome is a 501 (c) (3) non-profit organization that is the first public FMT stool bank in the United States for CDI non-responsive to standard therapy. Under the FDA's current regulatory framework of enforcement discretion, OpenBiome has partnered with more than 100 health care institutions in over 30 states to expand safe, affordable access to FMT. Accordingly, our institute is uniquely positioned to meaningfully assess the safety profile of FMT, as our group and others have identified an absence of high-quality, prospective studies interrogating safety.²¹

II. General Investigational Plan

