1. FMT procedure-related adverse events from colonoscopy/sigmoidoscopy or enema (e.g. perforation, sedation related)

2. FMT material-related adverse events (e.g. transmissible infection, allergic reaction) 3. Short-term safety: Both solicited and unsolicited adverse events will be recorded by, telephone follow-up at Day 3 (+/- 2 days) and clinical assessment at Week 6 (+/- 2 weeks).

4. Long-term safety evaluations will focus on any new medical conditions/medications, which may be related or unrelated to FMT. This information will be elicited at the 6 month and 12 month follow-up telephone call and documented.

VI-A. Adverse Events Reporting

A. Definitions

1. Adverse Event (AE)

An AE is any untoward medical occurrence in a patient or study subject administered FMT that does not necessarily have a causal relationship with this treatment. An AE can therefore be any unfavorable and unintended sign (including an abnormal laboratory finding), symptom, or disease temporally associated with the use of a FMT, whether or not related to the FMT.

• AEs may be new events or may be pre-existing conditions that have become aggravated or have worsened in severity or frequency.

• AEs may be clinically significant changes from baseline in physical examination, laboratory tests, or other diagnostic investigation (e.g. laboratory results, radiographic findings).

Pregnancy is not an AE; however, if a female subject becomes pregnant during the conduct of the study, the Investigator will notify Sponsor who is responsible for notifying the FDA.

2. Serious Adverse Event (SAE)

A serious adverse event is any adverse experience occurring during or after FMT that results in any of the following outcomes:

• Death

• Life-threatening experience

Note: An adverse event or suspected adverse reaction is considered "life-threatening" if, in the view of either the Investigator or Sponsor, its occurrence places the patient or subject at immediate risk of death. It does not include an adverse event or suspected adverse reaction that, had it occurred in a more severe form, might have caused death.

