• Requires inpatient hospitalization or prolongation of existing hospitalization Note: Adverse events requiring hospital admissions that are less than 24 hours in duration do not meet this criterion. A scheduled hospitalization for a pre-existing condition that has not worsened during participation in the study does not meet this criterion. Pre-planned hospitalizations for an elective medical/surgical procedure or routine check-ups do not meet this criterion. Admission for CDI relapse will not be included in this definition.

- Results in persistent or significant disability or incapacity
- Results in a congenital anomaly or birth defect

• Results in an important medical event

Note: Important medical events are those that may not be immediately life threatening or result in death or hospitalization but may jeopardize the patient or may require intervention to prevent one of the outcomes listed in the definition above.

3. Planned Hospitalization

A hospitalization planned prior to FMT is to be considered a therapeutic intervention and not the result of a new SAE. If the hospitalization or procedure is executed as planned, it will be recorded in the subject's medical history or procedures. However, if the event/condition worsens during the study, it must be reported as an AE.

4. Adverse reaction

An adverse reaction means any adverse event caused by FMT. Adverse reactions are a subset of all suspected adverse events for which there is reason to conclude that FMT caused the event.

5. Suspected Adverse Reaction

Suspected adverse reaction means any adverse event for which there is a reasonable possibility that FMT caused the adverse event. For the purposes of IND safety reporting, 'reasonable possibility' means there is evidence to suggest a causal relationship between FMT and the adverse event. A suspected adverse reaction implies a lesser degree of certainty about causality than adverse reaction, which means any adverse event caused by a therapy.

6. Unexpected

An adverse event or suspected adverse reaction is considered "unexpected" if it is not listed in the Investigator brochure or is not listed at the specificity or severity that has been observed; or is not consistent with the risk information described in the general investigational plan or elsewhere in the current application.

VI-B. Solicited Adverse Events

Short-term

The following short-term AEs and their associated intensities will be solicited:

- Fever
 - Mild 37.7-38.6°C

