 - Mild: Transient or intermittent episodes of unformed stools OR increase of ≤3 stools over baseline per 24-hour period
 - Moderate: persistent episodes of unformed to watery stools OR increase of 4-6 stools over baseline per 24-hour period
 - Severe: Bloody diarrhea OR increase of ≥7 stools per 24-hour period OR IV fluid replacement indicated

- Potentially Life Threatening: Life-threatening consequences (e.g. hypotensive shock)
- Nausea
 - Mild: Transient (<24 hours) or intermittent nausea with no or minimal interference with oral intake
 - Moderate: Persistent nausea resulting in decreased oral intake for 24-48 hours
 - Severe: Persistent nausea resulting in minimal oral intake for >48 hours OR aggressive rehydration indicated (intravenous fluids)
 - Potentially Life Threatening: Life-threatening consequences (e.g. hypotensive shock)
- Vomiting
 - Mild: Transient or intermittent vomiting with no or minimal interference with oral intake
 - Moderate: Frequent episodes of vomiting with no or mild dehydration
 - Severe: Persistent vomiting resulting in orthostatic hypotension OR aggressive rehydration indicated (intravenous fluids)
 - Potentially Life Threatening: Life-threatening consequences (e.g. hypotensive shock)

Long-term

The following long-term AEs and relevant details will be solicited:

- Gastrointestinal disorders
 - Inflammatory bowel disease
 - Irritable bowel syndrome
 - Celiac disease
 - Colon cancer
- Chronic infectious diseases (no therapy, outpatient, inpatient, ICU care)
- Autoimmune diseases
 - Inflammatory arthritis
 - Thyroid disease
 - Connective tissue diseases
 - Idiopathic thromobocytopenic purpura
- Metabolic disease
 - Diabetes Type 2 (diet controlled, oral hypoglycemic, insulin, uncontrolled/complication associated)
 - Metabolic syndrome (including obesity independently)
 - Non-alcoholic fatty liver disease
- Neuro-psychiatric disease
 - Multiple sclerosis
 - Depression/Anxiety
- Cardiovascular disease
 - Myocardial infarction (NSTEMI/STEMI)

- Stroke
- Cardiovascular related death

VI-C. Monitoring of Adverse Events

Each subject will be monitored for the occurrence of AEs, including SAEs. Each subject will be followed for safety monitoring at each follow-up interval.

- Subjects will be questioned at each follow-up interval regarding stool
 patterns, abdominal pain, fevers, and subjective well-being. First, subjects
 will be questioned about the possible occurrence of adverse events in a

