There have been no confirmed infectious complications directly attributable to FMT reported in the literature to date aside from a speculation about a norovirus case although the donor was untested for this.²⁹ There have been two FMT cases of bacteremia, although the strength of the association is unclear, and both patients did well on antibiotic therapy. However, since the process involves infusion of one person's "body fluids" into another person, transmission of an infectious agent or other disease or condition remains a theoretical possibility. From infusion of donor microbiome, the patient/subject could potentially acquire risk factors for chronic diseases such as diabetes or inflammatory bowel disease. Risks will be minimized by a rigorous donor selection process and evaluative studies on stool and blood of the donor to exclude transmission of infectious agents prior to FMT. Subjects will be informed that the treatment or procedure may involve these theoretical risks and additional risks that are currently unforeseeable. There have been reported cases of inflammatory bowel disease flares post-FMT, but it is unclear if this was attributable, and these patients have been excluded from this study. Infusion of fecal material containing a potential agent to which the subject is allergic is also a concern and so patients with a history of severe (anaphylactic) food allergy will be excluded from this study.

VII-C. Potential Risks to Donors

This study also involves individuals (donors) recruited to donate stool for FMT. There are 3 areas of risk to the potential stool donor.

These include:

 Physical risks related to laboratory testing and the stool collection protocol
 Psychological risks related to both revealing and potentially learning sensitive information during donor screening process

3) Risks related to confidentiality and loss of privacy.

OpenBiome volunteer donors will be utilized. In order to exclude donors at high risk of passing infection, a Donor Risk Factor Questionnaire (*Appendix* 2) will be administered. This questionnaire contains sensitive and potentially embarrassing questions

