second recurrence treated with a pulsed vancomycin regimen.¹⁷ FMT is conditionally recommended for management of a third CDI recurrence; the recommendation is provisional in part because further clinical trials are ongoing and there is a lack of standardized longitudinal follow-up in patients post-FMT.¹⁷ The rationale for this multi-center, open-label, longitudinal cohort study is to improve certainty about the safety profile of FMT, and complement the established literature and on-going studies of the efficacy of FMT. The current body of literature suggests that the risks of FMT are low, and are linked to complications associated with delivery such as colonoscopy/sigmoidoscopy or to theoretical infectious and non-infectious risks. Given the established benefits of FMT and the paucity of high-quality safety data, the potential benefits of this study outweigh the risks of using this investigational product.

III. Summary of Previous Human Safety Experience

III-A Observational Data

A robust systematic review and meta-analysis of 11 observational studies with a total of 273 CDI patients did not report any adverse events attributable to the FMT material in variable follow-up from 3 weeks to 8 years.²¹ However, 3 studies that used upper gastrointestinal FMT indicated that the nasogastric/nasojejunal tube itself could not be ruled out in contributing to a suspected adverse event: upper gastrointestinal bleed, peritonitis, and possibly enteritis.²¹

A multi-center retrospective review (n=77) reported no definite FMT adverse events in follow-up between 3-68 months (mean 17 months). The authors did report 4 patients developing diseases of potential interest after FMT (peripheral neuropathy, Sjogren's disease, idiopathic thromobocytopenic purpura, rheumatoid arthritis) and 7 non-FMT related deaths. Interestingly, the study noted post-FMT improvement in a patient with pre-existing allergic sinusitis and one with "arthritis", with the type unreported.²⁴

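### Allergic reaction, which the protocol undertakes to capture, has no item of its own in the solicited adverse event list; peripheral neuropathy is a lesser gap of the same kind

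*Combined protocol and SAP*

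**What the plan says.** Protocol section VI (Adverse Event Monitoring), item 2, undertakes to capture "FMT material-related adverse events (e.g. transmissible infection, allergic reaction". Section VII-B returns to the subject: "Infusion of fecal material containing a potential agent to which the subject is allergic is also a concern".

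Section VI-B sets out what subjects will be asked about. The short-term part opens "The following short-term AEs and their associated intensities will be solicited" and the long-term part "The following long-term AEs and relevant details will be solicited". Section VI-C describes how this is done. Each contact starts with a general question about well-being, and the solicited questions follow if the answer is positive.

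The Data Collection section summarises the form items. Day 0 records immediate adverse events. Day 3 and Week 6 ask about complications of administration, infections, new conditions or medications, and changes in existing conditions. Months 6 and 12 ask about new serious events, new conditions or medications, and changes in existing conditions.

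Section 9, III-A, cites a retrospective review of 77 patients in which four developed diseases of potential interest: "peripheral neuropathy, Sjogren's disease, idiopathic thromobocytopenic purpura, rheumatoid arthritis".

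**The concern.** Allergic reaction is one of only two examples that the protocol gives of harm from the material itself. The other, infection, has its own prompts. Allergy has none, so a mild or delayed reaction is recorded only if the subject thinks to raise it in reply to an open question. Peripheral neuropathy is the one disease in the cited set of four with no entry in the long-term list.

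The stake is interpretation. Safety is the study's main objective, there is no untreated arm (section X), and the Data Analysis section plans raw events and crude rates. With nothing to compare against, the result depends on how fully events are ascertained. A low count for a harm with no prompt of its own is hard to read as reassurance.

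**Working it through.** The plan gives no figure on this point to reproduce. The check is a comparison of named harms with prompts.

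**Step 1: coverage.** The 11 short-term items are fever, chills, fatigue/malaise, anorexia, abdominal pain, bloating, gas, constipation, diarrhea, nausea and vomiting.

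| Harm or disease | Named in | Solicited item (VI-B) | Other prompt |
|---|---|---|---|
| Infection | VI, item 2 | Fever and chills; chronic infections (long-term) | Day 3 and Week 6: infectious complications, and separately non-serious new infections |
| Allergic reaction | VI, item 2; VII-B | None | Day 0 immediate events; complications prompt at Day 3 and Week 6, under serious events; open questions |
| Idiopathic thrombocytopenic purpura | 9, III-A | Named | New conditions |
| Rheumatoid arthritis | 9, III-A | Inflammatory arthritis | New conditions |
| Sjogren's disease | 9, III-A | Connective tissue diseases | New conditions |
| Peripheral neuropathy | 9, III-A | None (the neuro-psychiatric group has only multiple sclerosis and depression/anxiety) | New conditions |

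Allergic items number 0 of 11. Diseases covered number 3 of 4.

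**Step 2: follow one mild case.** Suppose hives appear two days after FMT and settle untreated.
- The Day 0 form is too early.
- At Day 3 the complications prompt is a sub-item of the serious event assessment, and the only sub-item for non-serious events concerns infections.
- Transient hives are not clearly a new medical condition, and no new medication was started.
- The topics that VI-C raises at every contact are stool pattern, abdominal pain, fever and well-being.
- If the subject mentions the hives in reply to the general question, VI-E requires the event to be recorded. A positive reply then leads to a list that does not contain allergy.

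Capture therefore depends on the subject raising it.

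**Step 3: follow a neuropathy.** A diagnosed case is a new medical condition and would be recorded at Month 6 or 12. Undiagnosed numbness might not be mentioned.

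**Step 4: what numbers can be given.**
- *Allergy.* The documents give no rate. If none were recorded in 150 subjects, the one-sided 95% upper bound is 1 − 0.05^(1/150) = 1.98%. It is valid only if every reaction would have been recorded.
- *Neuropathy.* Take one case in 77 patients followed for a mean of 17 months (one case per listed disease is assumed). That is 1 case in 77 × 17 = 1,309 patient-months. This study offers at most 150 × 12 = 1,800. At a constant rate without dropout, the expected count is 1,800 / 1,309 = 1.4, and the chance of no case is exp(−1.375) = 0.25. So even with complete capture, a zero count would say little.

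**The case against.** The strongest reply is that these harms are actively sought. A reader might infer from the omission that both are left to the kind of reporting that the Introductory Statement criticises in earlier studies, namely events "spontaneously reported rather than actively sought, in turn increasing the risk of underreporting". The documents do not support that. Staff start the enquiry at all four follow-up contacts, new conditions and medications are asked about each time, unsolicited short-term events are recorded, and VI-E requires every adverse event to be entered. This part of the reply stands. What is missing is an item-specific prompt, not the enquiry.

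On allergy, the reply adds that an acute reaction would most plausibly appear on Day 0, when immediate events are recorded, and that eligibility already reduces the risk. The first part narrows the gap to mild or delayed reactions. The second helps less. VII-B excludes a history of severe food allergy; the exclusion criterion is narrower, applying where the allergen cannot be confirmed absent from the donor's diet. These two passages must be reconciled, and neither addresses milder allergy.

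On neuropathy, the cited review found no definite FMT adverse event, and the protocol does not itself call neuropathy a harm of FMT. That stands and is one reason why the point is secondary.

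A reader might also try to state how many cases would be missed. Scaling 1/77 directly to 150 subjects gives 150/77 = 1.95 cases and a (76/77)^150 = 14% chance of none, but that ignores 17 against 12 months of follow-up. The exact 95% interval for 1/77, 0.03% to 7.0%, corresponds to about 0.05 to 10.5 cases in 150. Any estimate of missed cases also needs a capture rate, which the documents do not give.

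Finally, the forms in Appendix 4 are not in the text available and may carry more prompts than the summary shows.

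**Conclusion.** The point holds as a gap in item-level ascertainment. Allergic reaction is named for capture, yet appears in none of the 11 short-term solicited items and in no Day 3 or Week 6 item. Mild or delayed reactions rely on open questions. Peripheral neuropathy, the one uncovered disease of four, is the lesser part, because the new-conditions prompt should catch a diagnosed case.

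The number of events lost cannot be estimated from the documents. The conclusion assumes that open questions may be less sensitive than itemised ones and that the Appendix 4 forms match the Data Collection summary. The change is worth making because it costs almost nothing in an uncontrolled study whose result is a set of event counts.

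**What to change.** 1. Add allergic reaction (rash, hives, swelling, wheeze), with intensity grades like the other short-term items, to the short-term list in VI-B. Add it to the Day 3 and Week 6 items as well, outside the serious event heading.
2. Add peripheral neuropathy to the long-term list in VI-B and to the Month 6 and Month 12 calls.
3. Change VI-C so that the itemised questions are put to every subject whatever the answer to the general question. Without this, the two new items would sit behind the same gate as the existing ones.
4. Check the Appendix 4 forms against the revised lists before they are final.

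No visit, test or treatment changes. Calls become slightly longer and adverse event counts may rise slightly.

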A. Donor Clinical Assessment: OpenBiome utilizes adult, healthy, universal donors who have given informed consent with oversight from Massachusetts Institute of Technology (MIT) IRB/COUHES. Refer to the OpenBiome Master File (BB-MF 15543) for donor selection details. An accompanying authorization letter from OpenBiome can be found in Appendix 1. The OpenBiome Donor Risk Factor Questionnaire (Appendix 2) is detailed elsewhere. Briefly, the Donor Risk Factor Questionnaire is modified from a similar questionnaire developed by the American Association of Blood Banks for blood donors. The stool donor questionnaire is used to exclude potential donors with infectious disease risk factors (eg. high risk sexual behavior, risk factors for variant Creutzfeldt-Jakob disease, high risk travel), medications that may mediate the microbiome, and a wide array of medical conditions that may have a theoretical link the microbiome.

B. Donor Laboratory Screening: Refer to the OpenBiome Master File (BB-MF 15543) for donor laboratory screening details. An accompanying authorization letter from OpenBiome can be found in *Appendix 1*. Briefly, both serologic and stool test are completed on prospective donors. All tests are outsourced to third-party Clinical Laboratory Improvement Amendments (CLIA)-certified testing facilities. As a condition for participation in this program, donors are required to submit written authorization for the disclosure of these test results to the OpenBiome, in compliance with the Health Insurance Portability and Accountability Act (HIPAA).

C. Donor Monitoring: Refer to the OpenBiome Master File (BB-MF 15543) for donor monitoring details. An accompanying authorization letter from OpenBiome can be found in *Appendix 1*. Briefly, the OpenBiome Donor Prospective Health Status Questionnaire (*Appendix 3*) details the routine questions asked before processing of a specimen, with initiation of clinical assessment by the Chief Medical Officer if a positive answer disclosed by a donor.

Subject preparation: determining eligibility, pre-treatment, and special considerations A. Subject Clinical Assessment

1. Potential subjects will undergo a medical interview to determine eligibility for the study and a physical exam will be performed at the screening visit.

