2. Baseline status, at MD discretion, will be conducted: HIV (type 1 and 2), hepatitis A (IgM, G), hepatitis B (HBsAg, anti-HBcIgM and anti-HBcIgG), hepatitis C (HCV antibody), and Treponema pallidum screening (EIA with reflex to RPR).

3. Baseline complete blood count, liver function panel, creatinine and random blood glucose, and stool *C. difficile* PCR will be documented prior to FMT.

B. Pre-Treatment Medications

1. Subjects will complete at least a 10 day course of vancomycin or fidaxomicin for the most recently diagnosed acute CDI prior to undergoing FMT.

2. To minimize symptoms, antibiotic therapy will be continued by subjects until 3 days prior to the FMT procedure then subsequently discontinued.

3. Any probiotics will be continued by subject until 3 days prior to the FMT procedure then subsequently discontinued.

4. The day before the procedure, the subject will be prepped with standard bowel prep if undergoing colonoscopic/sigmoidoscopy delivery at MD discretion. Patients receiving FMT via enema administration need not undergo a bowel prep at MD discretion.

C. Specimen Collection

Patients must be willing and able to provide stool samples for microbial characterization via high-throughput 16S rRNA sequencing. Patients will be asked to provide a baseline stool sample prior to the FMT procedure (Day 0), as well as follow-up stool samples collected at Day 3, Week 6, Month 6 and Month 12 after FMT.

Samples will be collected with a standard stool collection hat. Immediately after passage, approximately 1 gram of stool will be suspended in 5 ml of RNALater (Life Technologies) using a para-pak collection vial with embedded scoop (Meridian Biosciences). Samples will then be shipped at room temperature to the OpenBiome study site where they will be frozen within 7 days of passage, consistent with the technical specifications for stabilization of nucleic acids in RNAlater. To avoid contamination of the OpenBiome production facility, sample processing and sequencing will take place at the Massachusetts Institute of Technology in a BL-2 laboratory with appropriate containment.

D. Female Subjects:

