- Once at the most proximal location, 250 mL of the fecal material will be passed through the endoscope channel using a sterile syringe.

- Standard normal saline flush(s) will be utilized after all the fecal material has been infused.
- 2. Enema
 - The procedure will be completed by a trained Registered Nurse, Physician Assistant, or physician in an outpatient clinic, endoscopy recovery area, or standard endoscopy unit.
 - Fecal material will be transferred into conventional enema bottle/bag.
 - Patient will be placed in left lateral decubitus position with foot of bed elevated to facilitate retention.
 - Lubricated enema nozzle will be inserted into rectum and contents expelled into the distal colon with the subject requested to retain material for at minimum 30 minutes but targeting 1 hour.
 - The patient will be asked to transfer to right lateral decubitus position after 15 minutes. If unable to retain material for 1 hour, total retention time will be recorded.

Baseline assessment and follow-up

1. Subjects will be instructed to contact the clinical team if any symptoms of diarrhea occur or any adverse events occur. Follow-up assessments will focus on capturing any serious adverse events, new medical conditions, or changes in patients' pre-FMT medical conditions since last study contact.

2. After passing eligibility assessment, subjects will be assessed at baseline (Day 0 = day of procedure) to capture and document clinical and FMT characteristics (Appendix 4).

3. A study representative will contact subjects at Day 3 (+/- 2 days) post-FMT (Appendix 4).

4. An in-person clinical assessment between Week 6 (+/- 2 weeks) post-FMT will be performed by FMT provider (Appendix 4). If this visit cannot be arranged, the patient's primary care provider may complete the assessment under the guidance and instruction of the FMT provider.

5. A study representative will contact subjects at Month 6 (+/- 2 weeks) and Month 12 (+/- 2 weeks) post-FMT (Appendix 4).

6. A study representative will contact subjects to remind them to collect and mail stool samples.

7. A full Subject Contact Schedule (Appendix 5) and Informed Consent (Appendix 6).

In the event of clinical non-response

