- Demographics: Age, sex, race/ethnicity
- Pre-existing medical conditions
- Concomitant medications
- Vital signs including height, weight, calculated body mass index (BMI)
- CDI History, including:
 - o Date of initial CDI diagnosis
 - Number of CDI recurrences since initial diagnosis
 - o Baseline clinical symptoms and severity related to CDI
 - CDI treatments received to date

Section 2: FMT Procedure

- Study patient identifier
- Date
- Description of FMT procedures, including:
 - Route of administration (colonoscopy/sigmoidoscopy or enema)
 - Location in colon where FMT delivered
 - Sedation (if applicable)
 - Prep quality (if applicable)
 - Findings of colonoscopy (if applicable)
- Dose
- Unit ID/Lot# of each treatment
- Expiration Date
- Storage Condition
- FMT retention time (if less than 1 hour)
- Immediate adverse events

2. Short-term assessment I (Day 3 – Telephone Assessment)

- Study patient identifier
- Date
- Any change in baseline clinical symptoms related to CDI
- Assessment of SAEs, including:
 - Any complications related to FMT administration
 - Any potential infectious complications such as transmissible enteric infections, sepsis, peritonitis, or bacteremia
 - Any non-serious newly diagnosed infections (specific organism and body site)

- Any new medical conditions / new medications with associated clinical course
- Any changes in pre-existing medical conditions with associated clinical course
- 3. Short-term assessment II (Week 6 Clinical Assessment)
 - Study patient identifier
 - Date
 - Vital signs including height, weight, calculated body mass index (BMI)
 - Any change in baseline clinical symptoms related to CDI including documentation of clinical cure or clinical non-response
 - Assessment of SAEs, including:
 - Any complications related to FMT administration
 - Any potential infectious complications such as transmissible enteric infections, sepsis, peritonitis, or bacteremia.
 - Any new non-serious diagnosed infections (specific organism and body site)
 - Any new medical conditions / new medications with associated clinical course
 - Any changes in pre-existing medical conditions with associated clinical course

4. Long-term assessment I (Month 6 – Telephone Assessment)

- Study patient identifier
- Date
- Self-reported height and weight, resulting calculated BMI
- Any recurrence of CDI with description of clinical course, including additional treatments received
- Assessment of any new SAEs

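### Most solicited short-term symptoms have no listed pre-FMT grade, and the baseline for stool counts has no defined period, so new or worsened cannot be verified and count-defined diarrhea may be under-graded

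*Combined protocol and SAP*

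**What the plan says.** All references are to part 6 (Protocol) of the combined document.

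- **Definition of an event (VI-A, Adverse Event).** "AEs may be new events or may be pre-existing conditions that have become aggravated or have worsened in severity or frequency".
- **Diarrhea grades (VI-B, Short-term).** Moderate is "persistent episodes of unformed to watery stools OR increase of 4-6 stools over baseline per 24-hour period". Mild has the same two-armed form: transient or intermittent unformed stools, or a rise of up to 3 over baseline. Severe is blood in the stool, a rise of at least 7 a day, or a need for intravenous fluid.
- **Baseline timing (IV, Baseline assessment and follow-up, item 2).** "subjects will be assessed at baseline (Day 0 = day of procedure").
- **Baseline symptom data (V, Data Collection, Baseline Assessment).** One symptom item is listed: "Baseline clinical symptoms and severity related to CDI". Vital signs, pre-existing conditions and medications are also collected.
- **Bowel prep (IV, Pre-Treatment Medications, item 4).** "The day before the procedure, the subject will be prepped with standard bowel prep if undergoing colonoscopic/sigmoidoscopy delivery at MD discretion". For the other route, "Patients receiving FMT via enema administration need not undergo a bowel prep at MD discretion".
- **Earlier contact (IV, Subject Clinical Assessment, item 1).** "Potential subjects will undergo a medical interview to determine eligibility for the study and a physical exam will be performed at the screening visit". No symptom grading is listed there.
- **Recording and analysis.** Section VI places the recording of solicited and unsolicited short-term events at Day 3 and Week 6. The Data Analysis section reports safety as raw events and crude rates for the whole cohort.

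**The concern.** Whether a symptom is new or worse is a comparison with its state before FMT. For most solicited symptoms the listed data hold no earlier value on the same scale, and for stool frequency the plan does not say which day or period is the reference.

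This matters more here than in a controlled trial. Section X concedes that there is no untreated arm and that risk above background is hard to discern. For short-term symptoms, the subject's own earlier state is the main control within the study. Overlap is to be expected: the introduction describes CDI itself as causing diarrhea and abdominal pain, antibiotics stop 3 days before FMT, and section VII-B says that discomfort and gas pain can follow endoscopy. Without pre-FMT grades, the Specific Aim 1 symptom rates cannot separate continuing symptoms from emergent ones, and the causality assessment in VI-D has to rely on recall. The gap also cannot be filled reliably after FMT.

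**Working it through.** The plan gives no figure on this point to reproduce. The check is a comparison of sections, followed by two illustrations on stated assumptions.

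**1. Which solicited symptoms have a listed pre-FMT value?** VI-B solicits 11 short-term symptoms.

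- Fever: plausibly covered by Day 0 vital signs, and a temperature above 38 °C is an exclusion.
- Diarrhea and abdominal pain: plausibly covered by the CDI symptom item, though no scale or stool count is named.
- Chills, fatigue, anorexia, bloating, gas, constipation, nausea, vomiting: no listed item grades them.

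That leaves 11 − 3 = 8 symptoms without a listed grade. Several VI-B scales (chills, fatigue, abdominal pain, bloating, gas) describe current interference with activities, so an unchanged symptom fits a grade.

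**2. What could this do to a crude rate?** Let *p* be the share of subjects with an unchanged pre-existing symptom, *e* the rate of new onset in the rest, and *c* the share of unchanged symptoms recorded as events.

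Recorded rate = *p* × *c* + (1 − *p*) × *e*

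The documents give none of these. Assume *e* = 10% and *p* = 20% to 40%.

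- *c* = 0 (VI-A applied perfectly): 0.80 × 0.10 = 8%, or 0.60 × 0.10 = 6%.
- *c* = 1 (every unchanged symptom recorded): 0.20 + 0.08 = 28%, or 0.40 + 0.06 = 46%.

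The second line is an assumed worst case, not an estimate. Without pre-FMT grades the data cannot show where between these limits a reported rate lies.

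**3. What could a prep-affected stool count do?** Grade by count = post-FMT count − reference count, with cut-offs 1–3 mild, 4–6 moderate, 7 or more severe. The severe line does not repeat the words about baseline; I read it in the same way. Assumed usual count: 2 a day. Assumed prep-affected counts: 5 to 15 a day.

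| Reference | 9 a day after FMT | 6 a day after FMT |
|---|---|---|
| 2 (usual) | +7, severe | +4, moderate |
| 5 | +4, moderate | +1, mild |
| 8 | +1, mild | −2, none |
| 10 | −1, none | −4, none |
| 15 | −6, none | −9, none |

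This is the count arm alone. The other arm sets a floor: unformed stools are mild if transient or intermittent, and moderate if persistent, whatever the reference. So 9 unformed stools a day against a reference of 8 ends as mild or moderate, not severe, unless there is blood or a need for intravenous fluid. Six persistent unformed stools a day stay moderate. The shift is not universal either: 12 a day against 5 is +7, still severe.

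**The case against.** A reader might infer two stronger things, and the documents support neither.

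The first is that existing symptoms count as adverse events by rule. They do not. VI-A names pre-existing conditions as events when they have worsened, Day 3 and Week 6 ask about change in CDI symptoms, and VI-D lists pre-existing conditions among the alternative causes. VI-C opens with a general question and asks the solicited ones only after a positive answer. Subjects must also have improved on vancomycin or fidaxomicin to enter. All this makes full counting of unchanged symptoms unlikely. It does not supply the missing comparison: the rule is stated, but for most symptoms it cannot be checked.

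The second is that diarrhea after endoscopic FMT is missed. It is not, if the grades are applied as written, because the unformed-stool arm needs no baseline. Nor does the plan prescribe a prep-day count. It lists no count at all, and prep is at the physician's discretion. What stands is that the period is undefined, Day 0 is the only baseline defined, and a severe grade resting on count alone is exposed.

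The Specific Aim 1 hypothesis concerns related serious events, and section X puts the focus there. Delivery route is a subgroup for cure, not safety, so no planned safety comparison is biased by route. That limits the weight of the point. But adverse events are a listed safety endpoint, and the introduction faults earlier studies for not seeking events actively. Finally, the Appendix 4 forms may hold baseline items that the protocol text does not list.

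**Conclusion.** The point holds as a gap in measurement and definition, worth correcting but not fatal. On the listed data, new or worsened status cannot be verified for 8 of 11 solicited symptoms, and unchanged symptoms may enter the crude rates. The size of that effect is unknown; the 28% to 46% worst case rests wholly on assumed inputs. For diarrhea, an undefined reference that follows prep in prepped endoscopy recipients, but usually not in enema recipients, could lower the grade, chiefly from severe to moderate or mild when severity rests on count alone. The size again depends on assumed stool counts. The conclusion assumes that Appendix 4 adds no pre-FMT grading of these symptoms.

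**What to change.** 1. Complete the VI-B short-term symptom form once before any bowel prep, for example at the screening visit, for all delivery routes.
2. In VI-B, define baseline stool frequency as that pre-prep 24-hour count, and state that it applies to the mild, moderate and severe count criteria alike.
3. In Data Analysis, report solicited symptoms that were absent before FMT or have a higher grade after it, beside the raw post-FMT prevalence.

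The cost is one extra use of an existing set of questions, a few minutes at a visit that already takes place, one definition and one extra table. A limitation is that symptoms at screening may be suppressed by antibiotics, which stop only 3 days before FMT. The form should therefore carry its date and current CDI treatment. If Appendix 4 already grades these symptoms before prep, only the definition and the reporting rule are needed.
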